Data Analysis Plan: To quantify the effects of our POWER training intervention on neural and muscular adaptations, we will utilize repeated measures mixed effects regression models to assess for significant changes in our outcomes over time. Neural and muscular adaptations (on both the paretic and non-paretic legs) will serve as dependent variables in separate models, with time serving as the key independent variable in each. Various error structures associated with the repeated measures over time will be considered (e.g. compound symmetry vs. auto-regressive), and final error structures will be selected based on AIC values. Having random subject effects in the models will account for correlation among measures within subjects over time. Secondary analyses, incorporating differences in the paretic and non-paretic legs as dependent variables, will examine whether changes over time are more pronounced in the paretic vs. non-paretic leg. These models will also incorporate random subject effects to account for within-subject dependence. Error correction will be set to maintain type one error at 5% with a desired power of 80%.

Expectation: We hypothesize that POWER training will result in significant increases in muscle peak power generation, central activation, muscle CSA and in-vivo oxidative capacity as well as a concomitant decrease in [Pi]. Further, we expect changes in these variables will be greater in the paretic compared to the non-paretic leg. We also expect improvements in Clinical Assessments as a result of training as well as increases in our measures of locomotor function (see **Procedures-Specific**).

Innovation: Through conduct of the proposed experiments, we will generate a rich data set, capable of relating measures of lower extremity power generation (both in and away from the task of walking) with functional walking performance. The proposed neuromuscular assessment

[figure not shown]

Figure 13: Timeline for measures during POWER training

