Rationale: Given that in persons post-stroke, improving walking is 1) independently related to overall health status; 2) a strong predictor of functional recovery and 3) the most often stated goal during rehabilitation, interventions aimed at improving functional walking status are critical to increasing independence and improving quality of life for patients and their caregivers. The advanced methodologies proposed herein and the novel theoretical framework we have developed allow for detailed investigation of the neural and muscular factors that contribute to (changes in) muscle power generation. In addition, the state-of-the-art assessments of walking provide a comprehensive evaluation of locomotor behavior and the biomechanical mechanisms underlying hemiparetic walking performance. Moreover, we seek to identify the muscular characteristic(s) that best predict functional improvement and provide evidence establishing the characteristics of those most likely to benefit (or not) from training.

Summary of Experiment & Research Design: We will determine the relationship between changes in neural and muscular factors and improved power generation following training. We will also assess functional improvements via the proposed clinical assessments as well as through full biomechanical evaluations of walking.

Data Analysis Plan: We will assess relationships for changes in central activation, muscle CSA and [Pi] (predictor variables) with improvements in muscle power generation (criterion variable) and self-selected walking speed by using mixed effects regression models, which, by incorporating random subject effects, will allow us to account for correlation of measures made on the same individual over time. We will also use measures of muscle power generation in the paretic and non-paretic knee extensor and plantar flexor muscle groups as predictor variables in a multivariable linear regression model to assess relationships with self-selected walking speed. Standardized β coefficients from these regression models will help us determine which factors have the strongest influence on our outcome variables (i.e. power generation and self-selected gait speed).

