Sample size determination and Statistical Approach: A total of 28 subjects will be recruited for this study. With baseline data from n=28 subjects, we will have at least 80% power to detect measures of association (i.e. partial correlations) as small as 0.5 between neural/muscular adaptations and peak power generation. Our preliminary data suggest that the intraclass correlation between measures of power on paretic and non-paretic legs is extremely high (i.e. Spearman rho = 0.81, intraclass correlation coefficient [ICC - from mixed model] ~100%). This power estimate for Aim 1 is based on 1 observation per subject; although our mixed model approach for analyses for Aim 1 will include 2 observations per subject (i.e. paretic and non-paretic leg), the detectable correlation may not be substantially lower due to the strong intraclass correlation. For Aims 2 and 3, analyses rely on longitudinal measures, and we assume (based on experience with our patient population) that no more than 15% will fail to complete all assessments. With 28 subjects enrolled and a 15% attrition rate over time (resulting in complete data on 24 subjects), we would have at least 80% power to detect changes in measures from baseline to the end of the study equivalent to 0.6 standard deviation units (i.e. effect sizes). This power estimate is based on a paired t-test framework (i.e. pre-post comparisons), and thus power is likely underestimated, since our models will also include data from mid-intervention and follow-up time periods. For example, assuming an ICC of 90% associated with within-subject responses over 4 time periods, the effective sample size (see Campbell et al., 2001) would be slightly higher (~n=26), as would be our power (~83%) to detect an effect size of 0.6. Treatment effect sizes of 0.6 are consistent with our preliminary data, in which effect sizes of 0.7 (95% CI 0.5 to 0.9), 1.5 (95% CI 1.1 to 1.9, and 0.5 (95% CI 0.1 to 1.0) were observed for improvement in gait speed, paretic leg power, and non-paretic power, respectively. With complete data on 24 subjects, we will also be able to detect whether as little as 40% of the variability in changes in gait speed can be explained by changes in the neural / muscular adaptation measures, assuming an ICC of 90% associated with within-subject responses over 4 time periods. All power estimates assume 2-sided hypothesis tests and an alpha level of 0.05 and were conducted by a biostatistician using PASS 2008 (NCSS, Kaysville, Utah).

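### The Aim 3 mixed models name no visit term, so if changes at several visits enter, a training trend shared by everyone can pass for an association (minor)

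*Combined protocol and SAP*

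**What the plan says.** The Aim 3 Data Analysis Plan (section D) assesses "relationships for changes in central activation, muscle CSA and [Pi] (predictor variables) with improvements in muscle power generation (criterion variable") and with self-selected walking speed. The models are mixed effects regressions which, "by incorporating random subject effects, will allow us to account for correlation of measures made on the same individual over time". The adaptation changes and the random subject effect are the only terms named. The output is used to rank factors: "Standardized β coefficients from these regression models will help us determine which factors have the strongest influence on our outcome variables".

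The Aim 2 Data Analysis Plan fits a separate model to each adaptation, "with time serving as the key independent variable in each", and adds random subject effects as well. Aim 3 repeats the second element but not the first.

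The specific aims place the Aim 3 measurements at four times: 0, 4 and 8 weeks of training, and 8 weeks afterwards. The sample size section states "For Aims 2 and 3, analyses rely on longitudinal measures". It sizes Aim 3 on how much of the variability in "changes in gait speed can be explained by changes in the neural / muscular adaptation measures, assuming an ICC of 90" per cent over four time periods. No passage says which visits' changes enter the Aim 3 models.

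**The concern.** Aim 3 asks whether people who gain more in an adaptation also gain more in power or walking speed. The Aim 2 hypothesis is that training moves all these measures: power, activation and cross-sectional area up, [Pi] down. With several changes per person and no visit term, the slope mixes two things: both measures moved on average between visits, and individuals' gains go together. Aim 2 already reports the first. All stroke participants are trained, so no untrained stroke arm separates the two. An adaptation with no individual-level link to walking could then be reported as related to it.

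**Working it through.** **1. The plan's own figures.** 28 × 0.85 = 23.8, so 24 completers. A two-sided 5% paired t-test with n = 24 and effect 0.6 has power 0.804 (stated: at least 80%). Effective n = 24 × 4 / (1 + 3 × 0.9) = 96 / 3.7 = 25.9 (stated: about 26), with power 0.836 (stated: about 83%). These reproduce. They concern pre-post change and are not in dispute.

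**2. Size of the shared shift.** Set the level SD to 1 and use the plan's ICC of 0.90. The SD of a change is √(2 × 0.1) = 0.447.
- Planning effect: the plan says "This power estimate is based on a paired t-test framework (i.e. pre-post comparisons"), so 0.6 is read in change-SD units: 0.6 × 0.447 = 0.27 level SD.
- Pilot walking speed (Preliminary Studies, n = 5): 0.58 ± 0.24 to 0.78 ± 0.28 m/s, so 0.20 / √((0.24² + 0.28²)/2) = 0.77 level SD.
- The plan lists pilot "effect sizes of 0.7 (95% CI 0.5 to 0.9), 1.5 (95% CI 1.1 to 1.9, and 0.5 (95% CI 0.1 to 1.0") for gait speed, paretic power and non-paretic power, without a unit. For gait speed, 0.20 / 0.28 = 0.71 suggests level SD; this is an inference.
- No pilot effect size is given for central activation, cross-sectional area or [Pi].

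**3. Time courses (assumed).** Share of the 8-week gain at 0, 4 and 8 weeks and follow-up: fast 0/0.8/1/0.9, middle 0/0.5/1/0.8, slow 0/0.3/1/0.6. The documents do not settle this. The pilot reports continuing walking-speed gains over 8 weeks, while the section on self-selected walking practice allows that neural changes could come quickly.

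**4. Mechanism.** Only differences between the post-baseline visits matter. Let c be the sum of squared deviations of the three post-baseline shares from their mean:
- fast: 0.1² + 0.1² + 0² = 0.020
- middle: 0.267² + 0.233² + 0.033² = 0.127
- slow: 0.333² + 0.367² + 0.033² = 0.247

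For unrelated measures on the same course, with shifts a (predictor) and b (outcome), the expected slope without visit is roughly a·b·c / (a²·c + 0.3). The 0.3 is the within-subject part, 2 × 0.1 = 0.2, plus the between-subject part, 3 × (0.1 + 0.1/3) = 0.4, weighted by 0.1/(0.1 + 3 × 0.1) = 0.25. For a = b = 0.6 on the slow course this is 0.0888 / 0.3888 = 0.23, where the truth is 0. If the gain is complete by week 4 and kept, c = 0 and the slope is 0.

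**5. False-positive rates.** Simulated REML random-intercept fits: n = 24, ICC 0.90, unrelated predictor and outcome, three changes from baseline, two-sided 5%. Ranges span separate simulation runs.

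| Shift, predictor / outcome (level SD) | Fast | Middle | Slow | With visit |
|---|---|---|---|---|
| 0.27 / 0.27 | 5-6% | 6% | 6-8% | 5-6% |
| 0.27 / 0.77 | 5-6% | 10% | 18-19% | 5-6% |
| 0.6 / 0.6 | 6% | 20% | 47-49% | 5-6% |

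- Fast gain half lost by follow-up (0/0.8/1/0.5): 7%, 10% and 20% for the three rows.
- Different courses, last two rows: 6-10% when one measure is fast and the other slow; 11-14% and 26-30% when one is middle and the other slow.
- Complete by week 4 and kept (shifts 0.6/0.7): 5%.
- One pre-post change per subject: 4-6%.

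**6. Ranking.** Take one factor with a true slope of 0.3 and a 0.27 shift, and one unrelated factor. If the unrelated factor and the outcome also shift 0.27, the unrelated factor ranks first in 5-7% of trials without visit and 7-8% with it: no distortion. If the unrelated factor shifts 0.6 and speed 0.77, it ranks first in 6/13/22% (fast/middle/slow) without visit and 7/8/9% with it.

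**The case against.** The plan is silent on visit rather than excluding it, and an analyst might add it unprompted. The Aim 3 design summary speaks of improvement following training, and the power calculation is pre-post, so one change per subject could be meant; then there is no bias. These points make the concern conditional. They do not remove it, because a random subject effect for measures over time has little purpose with one change each, and the sample size section refers to four time periods.

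It is also fair that at the plan's own effect size the inflation is negligible, and that the larger rates need shifts or courses the documents do not supply. That stands.

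Four stronger readings are tempting but unsupported:
- *The false-positive rate is generally very high.* Complete loss of the gain by follow-up (0/0.5/1/0), with shifts of 0.6 and 0.7 level SD, gives 93%, and entering visit levels instead of changes can give more. No passage supports that course, and the Aim 3 text describes changes, not levels.
- *The ranking of factors is generally distorted.* It is not when the factors shift equally (step 6).
- *A single pre-post change is a much weaker analysis.* That depends on where the association lies. With a slope of 0.3 that also links visit-to-visit variation, power is about 30% pre-post and 70-75% for three visits with visit in the model. If only person-specific gains are linked (assumed gain SD 0.45, correlation 0.8), it is 50-53% pre-post and 29-45% for the multi-visit model. The documents do not say which holds.
- *The disagreement over a follow-up power test is evidence for this point.* The Aim 2 design summary lists that test and the Dynamometric Assessment section does not. This needs reconciling in its own right, but using weeks 4 and 8 alone gives nearly the same rates.

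**Conclusion.** The concern holds in conditional form. As written, the Aim 3 mixed models leave a shared training trend in the association whenever changes at more than one visit enter and the mean changes differ between those visits. The false-positive rate is then about 5-8% at the plan's 0.6 change-SD in both measures, about 5-19% with a 0.27 SD predictor shift and the pilot walking-speed shift, and up to about 48% with 0.6 level SD in both on the slow course. With different courses for predictor and outcome it runs from about 6% to 30% among the pairs tried. It is nominal if the gain is complete by week 4 and kept, or with one change per subject.

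These rates are illustrations. They rest on assumed time courses, an assumed predictor shift, equal correlation between visits, the plan's ICC of 0.90, 24 completers and one predictor at a time. Aims 1 and 2, the stated sample size and the separate multivariable linear regression in Aim 3 are outside this point. Severity: minor.

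**What to change.** In every Aim 3 mixed model that uses more than one visit per subject, add visit as a categorical fixed effect next to the random subject effect, and state which visits' changes enter. With three changes per subject this costs 2 degrees of freedom, needs no new data and returns the error rate to about 5-6%. The coefficient then answers who gained more, not what moved on average.

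Alternatively, pre-specify one pre-post change per subject, which is equally unbiased. Choose according to whether the association is expected in visit-to-visit variation (several visits with a visit term does better) or only in person-specific gains (pre-post does as well or better).

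Separately, reconcile the Aim 2 design summary with the Dynamometric Assessment section on whether power is tested at follow-up, since that decides which visits are available.

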Summary: The consequences of alterations in skeletal muscle post-stroke are far reaching and contribute to decreased motor control and overall fitness, development of functional limitations, and long term disability. We have highlighted several adaptive changes that occur that contribute to muscle dysfunction in persons post-stroke when compared to neurologically healthy individuals. To date, however, the relative importance of these factors as well as whether and how these impairments relate to existing functional deficits is yet unknown. Furthermore, the extent to which these alterations are amenable to rehabilitation training and the degree to which changes in these properties relate to functional improvements would be valuable information to help guide therapeutic decision making in the treatment of post-stroke locomotor dysfunction.

Plantar flexor muscle power generation is associated with locomotor function post-stroke: Individuals following stroke typically present with some degree of residual motor function. The extent of this residual function varies greatly from person to person, and significant locomotor impairments often persist. Although a number of factors likely contribute to slow walking, we examined the importance of muscle power generating capacity of the plantar flexor muscle group during dynamometric strength testing in predicting locomotor ability in individuals with chronic post-stroke hemiparesis (n=23). Ankle plantar flexor power was determined bilaterally. In addition, self-selected gait speed was measured during over-ground walking. Significant correlations were

found between self-selected gait speed and ankle power in the paretic ($r = 0.78$) and non-paretic ($r = 0.46$) legs (Figure 5). The strength of the correlation between the paretic PF muscle group and gait speed suggests the importance of ankle power in predicting locomotor ability post-stroke and suggests paretic PF function as a potential target for improving locomotor ability in this large clinical cohort.

[figure not shown]

Figure 5: Correlations between self-selected gait speed and plantar flexor power in the paretic (left) and non-paretic (right) legs.

Paretic ankle powers relate to locomotor performance:

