Summary of Experiment & Research Design: We will perform comprehensive dynamometric, electrophysiological and magnetic resonance assessments of paretic and non-paretic musculature. Measurements will be performed on a total of 28 subjects at least six months following stroke and comparisons made to the dominant leg of a group of matched (age, gender, height & weight) neurologically healthy individuals (n=28). In doing so, we will determine if, and to what extent, neural and muscular factors differ between legs (paretic vs. non-paretic vs. control). In addition, we will determine the relationship between these factors and impaired muscle power generation. Our primary outcome measures in the ankle plantar flexor and knee extensor muscle groups will include 1) peak torque and power generation determined via isokinetic and isotonic dynamometry, respectively; 2) central activation measured using superimposed neuromuscular electrical stimulation; 3) muscle cross-sectional area (CSA) determined via MRI; and 4) muscle oxidative capacity (reflected by the rate of PCr recovery) and resting concentrations of inorganic phosphate [Pi] measured using ^{31}P MR spectroscopy.

Data Analysis Plan: The influence of neural and muscular adaptations (central activation, muscle CSA, *in-vivo* oxidative capacity and [Pi]) on peak power generation at baseline will be conducted using mixed effect regression models. The mixed models will be used with random subject effects to account for the dependent nature of the data collected on paretic and non-paretic legs within the same individuals. The baseline measure of peak power generation will serve as the dependent variable, with fixed effects for leg involvement (paretic vs. non-paretic) and for neural and muscular adaptation measures. Model fit will be assessed via Akaike Information Criteria (AIC). Partial correlations and standardized β coefficients will determine those factors with the strongest influence on muscle power generation. The models will also allow us to address secondary questions such as the differences between peak power generation and neural and muscular adaptation measures in paretic and non-paretic limbs.

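### In the Aim 3 leg-power regression, standardised betas are a poor measure of influence: on the plan's own correlations the non-paretic leg could get a negative beta despite a positive correlation with walking speed

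*Combined protocol and SAP*

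**What the plan says.** Section D, Aim 3, Data Analysis Plan describes two sets of models. The first relates changes in central activation, muscle cross-sectional area and [Pi] to improvement in power and to walking speed. The second, which is the subject here, takes power in the "paretic and non-paretic knee extensor and plantar flexor muscle groups as predictor variables in a multivariable linear regression model", with self-selected walking speed as the outcome. For both, the standardised betas will "help us determine which factors have the strongest influence on our outcome variables". Aim 3 names no other importance measure, no collinearity check, and no interval for the betas or their ranks.

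Two other places give the relevant correlations:

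- Section D, Sample size determination and Statistical Approach, states that the "intraclass correlation between measures of power on paretic and non-paretic legs is extremely high (i.e. Spearman rho = 0.81", with a mixed-model ICC of about 100%. The plan uses this only to argue that a second leg per subject adds little power for Aim 1.
- Section C, Preliminary Studies, reports significant correlations (n = 23) "found between self-selected gait speed and ankle power in the paretic ($r = 0.78$) and non-paretic ($r = 0.46$) legs".

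**The concern.** A standardised beta is a conditional slope: the expected difference in speed per SD of one predictor with the others held fixed. When two predictors move together as closely as the plan says the two legs do, that slope can be large, exceed 1, or take the opposite sign to the simple correlation. It remains a valid conditional estimate, but it no longer answers the question of how strongly a factor bears on the outcome.

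The training is given to each leg separately, and Aim 3 sets out to find which muscle characteristics best predict functional improvement. A negative beta for the non-paretic leg, presented as influence, could be taken to mean that non-paretic power works against walking speed. The plan's own pilot correlation for that leg is positive.

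**Working it through.** **The plan's own figures.** The plan states no standardised beta, so there is none to reproduce. Its sample size follows: 28 × 0.85 = 23.8, taken as 24 completers. Its 80% power for a 0.6 SD change also reproduces (paired t-test, n = 24: 80.4%), but it has no bearing on the ranking.

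**Inputs**

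- r1 = 0.78, speed with paretic PF power (Section C, n = 23)
- r2 = 0.46, speed with non-paretic PF power (same source)
- r12 = 0.81, between-leg power (Section D, sample size; Spearman, muscle group and n not given)
- n = 24 completers or 28 enrolled
- Assumption: the three correlations apply to one population and to levels of power.

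**Two-predictor standardised regression**

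- 1 - r12² = 1 - 0.6561 = 0.3439, so VIF = 1/0.3439 = 2.9
- Paretic beta: b1 = (0.78 - 0.81 × 0.46)/0.3439 = 0.4074/0.3439 = +1.18
- Non-paretic beta: b2 = (0.46 - 0.81 × 0.78)/0.3439 = -0.1718/0.3439 = -0.50
- R² = 1.185 × 0.78 - 0.500 × 0.46 = 0.694
- SE at n = 24: sqrt[(1 - 0.694)/(0.3439 × 21)] = 0.21; t = -2.4; 95% CI -0.93 to -0.07. At n = 28 the SE is 0.19.

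If these correlations were the true values, simulated studies of 24 would give a negative non-paretic beta in about 99% of samples.

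**When the sign turns.** b2 < 0 when r2 < r12 × r1, that is, when r12 > 0.46/0.78 = 0.59.

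| r12 | b1 | b2 |
|---|---|---|
| 0.50 | +0.73 | +0.09 |
| 0.59 | +0.78 | 0.00 |
| 0.70 | +0.90 | -0.17 |
| 0.81 | +1.18 | -0.50 |

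**Uncertainty in r2.** Fisher's z at n = 23 gives an approximate 95% CI for 0.46 of 0.06 to 0.73. With the other two values held fixed, b2 is zero at r2 = 0.81 × 0.78 = 0.63, and at r2 = 0.73 it is (0.73 - 0.6318)/0.3439 = +0.29. The upper end of the interval therefore removes the sign change.

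**Order.** b1 + b2 = (0.78 + 0.46)/1.81 = +0.69 and b1 - b2 = (0.78 - 0.46)/0.19 = +1.68. Both are positive, so |b2| < b1. The same holds for any r1 > r2 > 0.

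**Order-averaged R² on the same inputs**

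- Paretic: entered first 0.78² = 0.608; entered second 0.694 - 0.46² = 0.483; average 0.55
- Non-paretic: entered first 0.212; entered second 0.694 - 0.608 = 0.086; average 0.15

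The order is the same as with the betas, and both contributions are positive.

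**Partial correlation.** Non-paretic: -0.1718/sqrt(0.3439 × 0.3916) = -0.47. Adding partial correlations alone, as Aim 1 does, would leave the negative sign in place.

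**Four predictors (illustration only).** The documents give no KE correlations. Assume a between-leg correlation of 0.81, a PF-KE correlation from 0 to 0.8, R² = 0.6, and true betas all positive with the largest twice the next. At n = 24 the true top factor then ranked first in 57% down to 44% of simulated samples, and at least one beta had the wrong sign in 58% up to 85%. At n = 28 the ranges were 61% to 46% and 53% to 83%.

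**The case against.** Several objections have force.

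- *The order does not change.* A reader might infer that the betas put the wrong leg first. On the reported figures they do not, and cannot while both correlations are positive and the paretic one is larger. Order-averaged R² also puts the paretic leg first, in line with the plan's expectation about the paretic plantar flexors. Instability with four predictors is plausible, but it rests on assumed inputs. This stands.
- *Aim 1 is a different case.* A reader might extend the point to Aim 1, where partial correlations and standardised "coefficients will determine those factors with the strongest influence on muscle power generation". There power is the outcome, the legs are linked through a random subject effect, and the predictors are activation, cross-sectional area, oxidative capacity and [Pi]. The between-leg correlation of power says nothing about collinearity among those. The first Aim 3 models are outside it for the same reason. This stands.
- *The plan sets no rule that the largest beta wins.* It says the betas will help, and nowhere says that a negative coefficient will be read as harm. A negative slope at fixed paretic power is legitimate, and could be of interest given the plan's remarks on compensation. So the misreading could happen; the documents do not commit to it.
- *The inputs are mixed.* The 0.81 is a rank correlation for unspecified power measures, possibly from another sample, and it appears to concern levels. If the model uses changes, the documents give no between-leg correlation and the calculation does not apply. This limits certainty. The Spearman issue alone matters little: a Pearson equivalent near 0.82 gives +1.24 and -0.56.
- *A VIF of 2.9 is moderate.* True. The difficulty lies in reading betas as importance with few subjects, more than in extreme collinearity.

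**Conclusion.** The concern holds for one analysis: the Aim 3 regression of walking speed on the four leg-and-muscle powers. With predictors as correlated as the plan says, standardised betas are a poor gauge of influence. On its pilot figures the non-paretic leg would get about -0.50 against a simple correlation of +0.46, and the paretic leg +1.18.

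The sign reversal is likely rather than certain. It assumes one population for the three correlations, a two-predictor version of a four-predictor model, and levels of power. It would vanish if the non-paretic correlation were above about 0.63 or the between-leg correlation below 0.59.

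The documents do not show a wrong ranking, a fault in Aim 1, or an intention to conclude that non-paretic power slows walking. At n = 24 to 28 the four-factor ranking may be unstable, but the size of that cannot be derived from what is reported. This is a gap in how results would be interpreted and reported, worth closing because closing it is cheap.

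**What to change.** Keep the regression and amend the Aim 3 Data Analysis Plan as follows:

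1. State whether the leg-power model uses levels or changes.
2. Report standardised betas as conditional coefficients with confidence intervals, and do not call them influence.
3. Beside them, show each predictor's simple correlation with speed, the correlations between predictors, and the VIFs.
4. Add each predictor's R² contribution averaged over orders of entry (general dominance or Shapley), with bootstrap intervals for the contributions and their ranks. This measure carries no sign and answers a different question from the betas, so it supplements them.
5. Call a factor the strongest only if its interval separates from that of the next.

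The cost is a little more analysis, with no new data or visits. The drawback is that at n = 24 to 28 the intervals may overlap and the ranking may have to be reported as inconclusive.
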